9.4 Statistical Analyses

The initial statistical analysis plan (SAP) was finalized prior to the database lock for the interim analysis informing progression to Phase III for the Original Phase II Cohort; an amended SAP will be finalized prior to the database lock for any interim analysis applicable to the Supplemental Phase III Cohorts. Additional SAP amendments may be performed after execution of the interim analysis and before any additional analysis that occurs between any such interim analyses and the final analysis. The SAP will include a more technical and detailed description of the statistical analyses described in this section. This section is a summary of the planned statistical analyses.

The endpoints for safety and immunogenicity are as shown in [Table 3.1](#).

9.4.1 General Considerations

For the Original Phase II Cohort, analyses of safety and immunogenicity objectives will be descriptive. For the Supplemental Phase III Cohorts, hypothesis testing will be conducted for the primary immunogenicity objectives and conditional secondary objectives as described above. Analyses of other secondary objectives and exploratory objectives will be descriptive. Exploratory objectives will be included in either the SAP or supplemental SAP.

9.4.2 Statistical Considerations

9.4.2.1 Original Phase II Cohort

9.4.2.1.1 Primary - Safety

The main parameter will be described for all safety endpoints. The percentage of participants (using as denominator the number of participants) will be provided for analysis of solicited AEs, unsolicited AEs (including immediate systemic AEs within 30 minutes), SAEs, AESIs and MAAEs. The corresponding 95% CIs for the percentages will be calculated based on the Clopper-Pearson method. Subgroup analyses will be performed for age group, baseline SARS-CoV-2 Naïve status (Naïve at D01 and Non-Naïve at D01) (as defined in [Section 9.3](#)), and high-risk medical conditions group for the main safety analyses.

The SafAS population will be used for safety analyses for the following endpoints:

- Presence, and relationship of unsolicited (immediate) systemic AEs reported in the 30 minutes after each vaccination.
- Presence, time of onset, number of days of occurrence, intensity, action taken, and whether the reaction led to early termination from the study, of solicited (pre-listed in the participant's DC and CRF) injection site reactions and systemic reactions occurring up to 7 days after each vaccination.

- Presence, nature (Medical Dictionary for Regulatory Activities [MedDRA] system organ class [SOC] and preferred term [PT]), time of onset, duration, intensity, relationship to vaccination and whether the event led to early termination from the study of unsolicited AEs reported up to 21 days after the last vaccination.
- Presence, nature (MedDRA SOC and PT), time of onset, seriousness criteria, relationship to vaccination, outcome, and whether the event led to early termination from the study, of SAEs.
- Presence, nature (MedDRA SOC and PT), relationship to vaccination of all protocol-specified AESIs from the time of the first study vaccination throughout the study.
- Presence, nature (MedDRA SOC and PT), relationship to vaccination of MAAEs throughout the study.

9.4.2.1.2 Primary - Immunogenicity

The percentage of responders and participants having a 2-fold rise (2FR), 4-fold rise (4FR) will be provided against each endpoint with the corresponding 95% CIs using the Clopper-Pearson method. Differences of percentages of responders and participants with 2FR, 4FR will be provided with 95% CI calculated by the Newcombe-Wilson score method without continuity correction for the main immunogenicity analyses (65). GMTs in each injection group and GMT ratios between injection groups will be summarized along with their 95% CIs using the normal approximation of log-transformed titers. GMTs will be presented in original scale that are re-converted from log-transformed titers. GMTRs is defined as geometric mean of individual titers ratios (post-vaccination/pre-vaccination for each injection). GMTR will be summarized with 95% CI (normal approximation) for D36 compared to D01. Reverse Cumulative Distribution Curves (RCDC) will be generated for baseline (D01) and post-vaccination immunogenicity. Additional parameters may be displayed as appropriate.

The PPAS Naïve-D01+D22 will be utilized for primary immunogenicity endpoints. Subgroup analyses will be performed by age-group (18-59 years old and \geq 60 years old), and high-risk medical conditions groups. The primary immunogenicity endpoints will also be evaluated on FAS Naïve-D01 and FAS Naïve-D01+D22. Details of the analysis and any additional analysis will be described in the SAP if applicable.

9.4.2.1.3 Secondary – Safety

The occurrences of serologically-confirmed SARS-CoV-2 infection will be described by percentages of participants with infection during the analysis period with 95% CI by Clopper-Pearson methods. The occurrences of each endpoint related to laboratory-confirmed symptomatic COVID-19 will be described by percentages with 95% CI (by Clopper-Pearson methods). SafAS population will be utilized for analysis.

Participants with an active SARS-CoV-2 infection at baseline (as determined by positive NAAT at D01) will be listed separately, if applicable.

If the total number of observed COVID-19 clinical illness cases at the analysis time point is less than 5 in all groups, no summary analysis will be performed, and a listing of observed cases will be provided. Additional analyses will be described in the SAP.

9.4.2.1.4 Secondary - Immunogenicity

The same analysis methods stated in [Section 9.4.2.1.2](#) will be applied for both neutralizing antibody titers and binding antibody titers in all listed timepoints. Geometric mean value of concentrations (GMCs), GMC ratios and geometric mean concentration ratios (GMCRs) will be used for notations against binding antibody concentrations instead of GMT, GMT ratios and GMTR against neutralizing antibody titers. Analysis of 2FR, 4FR and proportion of responders in naïve and non-naïve will be estimated as described above.

The PPAS Naïve-D01+D22 and PPAS Non-Naïve-D01/D22 populations will be utilized for secondary immunogenicity endpoints. Analysis will also be performed in FAS Naïve D01+D22, FAS Naïve-D01, and FAS Non-Naïve-D01. Details of the analysis and any additional analysis will be described in the SAP if applicable.

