
1) To assess the neutralizing antibody profile at D22, D78, D134, D202, D292, and D387 in SARS-CoV-2 naïve adults in each study Intervention Group.
 
2) To assess the neutralizing antibody profile at D01, D22, D36, D78, D134, D202, D292, and D387 in each study Intervention Group for SARS-CoV-2 non-naïve participants.
 
3) To assess the binding antibody profile at D01, D22, D36, D78, D134, D202, D292, and D387 in each study Intervention Group in SARS-CoV-2 naïve and non-naïve participants.
	
Endpoints for secondary immunogenicity objectives #1 and #2: Neutralizing antibody titers will be measured in participants for each study Intervention Group against the D614G variant.
 
 • Individual serum neutralizing titer at each pre-defined time point • Individual serum neutralization titer fold-rise post-vaccination relative to D01 at each pre-defined time point • 2-fold-rise and 4-fold-rise in serum neutralization titer [post/pre] (fold-rise ≥ 2 and ≥ 4) at each pre-defined post-vaccination timepoint • Responders, defined as participants who had baseline values below LLOQ with quantifiable neutralization titer above assay LLOQ at each pre-defined post-vaccination timepoint and participants with baseline values above LLOQ with a 4-fold increase in neutralizing antibody titers at each pre-defined post-vaccination timepoint 
Endpoints for secondary immunogenicity objective #3: Binding antibody concentrations will be measured in participants for each study Intervention Group against the D614G variant.
 
 • Individual antibody concentration at each pre-defined time point • Individual antibody fold-rise post-vaccination relative to D01 at each pre-defined post-vaccination time point • 2-fold-rise and 4-fold-rise (fold-rise in antibody concentration [post/pre] ≥ 2 and ≥ 4) at each pre-defined post-vaccination time point • Responders, defined as participants who had baseline values below LLOQ with quantifiable antibody concentration above assay LLOQ at pre-defined post-

	vaccination timepoints and participants with baseline values above LLOQ with a 4-fold increase in binding antibody concentration at each pre-defined post-vaccination timepoint
Secondary Immunogenicity-Supplemental Cohort 1	

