8.3.4 ELECSYS Anti-SARS-CoV-2 Anti-N ECLIA

SARS-CoV-2 anti-nucleocapsid antibodies will be measured using the Roche ELECSYS Anti-SARS-CoV-2 ECLIA on all blood samples in participants for ascertainment of serologically-confirmed SARS-CoV-2 infection in participants belonging to the Original Phase II Cohort. In addition, this test will be used on D01 and D22 samples for the Original Phase II Cohort in all participants to aid in determination of naïve and non-naïve status (see [Section 8.1.5.3](#)). Details will be provided in the Operating Guidelines and the PPD laboratory manual.

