9.3 Analysis Sets

The following subgroup definitions of SARS-CoV-2 Naïve and Non-Naïve at D01 or both D01 and D22 timepoints are applied for all randomized participants in the Original Phase II Cohort:

Prior SARS-CoV-2 infection status (Original Phase II Cohort)	Description
SARS-CoV-2 Naïve at baseline (Naïve-D01)	
• Negative by the anti-S immunoassay (Roche Elecsys) on D01 serum sample AND 
• Negative by the anti-N immunoassay on D01 serum sample AND 
• Negative NAAT for SARS-CoV-2 on respiratory sample collected on D01
SARS-CoV-2 Non-Naïve at baseline (Non-Naïve-D01)	
• Positive by the anti-S immunoassay (Roche Elecsys) on D01 serum sample OR 
• Positive by the anti-N immunoassay on D01 serum sample OR 
• Positive NAAT for SARS-CoV-2 on respiratory sample collected on D01
SARS-CoV-2 Naïve at second injection (Naïve-D01+D22)	
• Negative by the anti-S immunoassay (Roche Elecsys) on D01 serum sample AND 
• Negative by anti-N immunoassay on D01 and D22 serum sample AND 
• Negative NAAT for SARS-CoV-2 on respiratory sample collected on D01 and D22
SARS-CoV-2 Non-Naïve at second injection (Non-Naïve-D01/D22)	
• Positive by the anti-S immunoassay (Roche Elecsys) on D01 serum sample OR 
• Positive by the anti-N immunoassay on D01 or D22 serum sample OR 
• Positive NAAT for SARS-CoV-2 on respiratory sample collected on D01 or D22

The following subgroup definitions of SARS-CoV-2 Naïve and Non-Naïve at D01 timepoint are applied for all randomized participants in all Supplemental Cohorts:

Prior SARS-CoV-2 infection status (Supplemental Cohorts)	Description
SARS-CoV-2 Naïve at baseline (Naïve-D01)	
• Negative by the anti-S immunoassay (Roche Elecsys) on D01 serum sample 
AND
 
• Negative NAAT for SARS-CoV-2 on respiratory sample collected on D01

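### Original Phase II Cohort: naïve status is last checked at D22, so titres raised by later infection enter the naïve antibody results from D78 to D387

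*Protocol*

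**What the plan says.** Secondary immunogenicity objective 1 for the Original Phase II Cohort (Section 3, Table 3.1) is: "To assess the neutralizing antibody profile at D22, D78, D134, D202, D292, and D387 in SARS-CoV-2 naïve adults in each study Intervention Group". Objective 3 asks for binding antibody over the same period.

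Section 9.4.2.1.4 names the populations: PPAS Naïve-D01+D22 and PPAS Non-Naïve-D01/D22 "populations will be utilized for secondary immunogenicity endpoints". It states that the methods of the primary analysis "will be applied for both neutralizing antibody titers and binding antibody titers in all listed timepoints". The supportive naïve sets it names are FAS Naïve-D01+D22 and FAS Naïve-D01.

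Section 9.3 defines Naïve-D01+D22 by a negative anti-S result at D01 together with two further conditions: "Negative by anti-N immunoassay on D01 and D22 serum sample" and "Negative NAAT for SARS-CoV-2 on respiratory sample collected on D01 and D22". None of the PPAS exclusion criteria in the same section concerns infection after the second injection.

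Section 8.3.4 has the anti-N assay run "on all blood samples in participants for ascertainment of serologically-confirmed SARS-CoV-2 infection in participants belonging to the Original Phase II Cohort", and Table 8.1 marks it at all eight visits. For results after D22, the only stated use is the safety percentage in Section 9.4.2.1.3.

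Two rules affect who is still sampled late. Exclusion criterion E17 (Section 5.2) keeps anyone with NAAT-confirmed infection after the first primary dose out of the booster groups. A footnote to Table 1.1 says V07 and V08 (D292 and D387) do not apply to participants who enrol in Supplemental Cohort 2.

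**The concern.** The secondary analysis is meant to show how vaccine-induced antibody persists over a year in people without prior infection. Membership of the set is settled at D22, while the last titre is taken a year after the second injection. Someone infected at month 4 remains in the set. Their raised titre counts in every later GMT, fold-rise and between-group ratio. It can also turn a participant whose vaccine antibody has waned back into a responder.

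If infection raises titres, late GMTs are too high and waning looks slower than it is. If infection is unequal between dose or age groups, the difference appears as a difference in durability. That matters here. Section 4.3 gives likely better durability at a higher dose as one reason for choosing 10 µg for Phase III, and Section 9.5 plans a second interim analysis on data to D202.

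No named analysis would reveal the mixing, because every naïve set stops at D01 or D22. The anti-N results that would identify infected participants are already collected.

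**Working it through.** **The plan's own figure.** Section 9.2.1 says 130 evaluable naïve participants per group allow a minimum observed GMT ratio of 0.73, for a true ratio of 1, log10 SD 0.67 and 95% probability.

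10^(−1.645 × 0.67 × √(2/130)) = 10^(−0.1367) = 0.730

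This reproduces. It corresponds to a difference of 1/0.73 = 1.37-fold.

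**Which visits are exposed.** The D22 sample is taken at the visit where anti-N and NAAT are also checked, so it is covered. D36 follows by 14 days and is barely exposed. D78, D134, D202, D292 and D387 are fully exposed.

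**Effect on the GMT.** Let f be the share of the naïve set infected after D22, and R the ratio of their titre to that of uninfected members. On the log scale the mean shifts by f × log R, so the GMT is multiplied by R^f.

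- R comes from Table 4.6 (18 to 59 years): non-naïve D22 over naïve D36 is 16962/2938 = 5.77 at 5 µg and 13039/3961 = 3.29 at 10 µg.
- f is not in the protocol. I assume 5%, 10% and 20%.
- For waning of the uninfected, Section 4.3 cites a 4- to 7-fold fall by 6 months for another vaccine. If infected titres do not fall at all, R runs from 3.29 × 4 = 13.2 to 5.77 × 7 = 40.4. This is an upper illustration.

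| f (assumed) | No waning, R = 3.29 to 5.77 | With waning, R = 13.2 to 40.4 |
|---|---|---|
| 5% | 1.06 to 1.09 | 1.14 to 1.20 |
| 10% | 1.13 to 1.19 | 1.29 to 1.45 |
| 20% | 1.27 to 1.42 | 1.67 to 2.10 |

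**Against the design figure.** The share that inflates the GMT 1.37-fold is f = ln(1/0.73)/ln R. That is 18% to 26% without waning and 9% to 12% with it.

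**Between dose groups.** A 10-point difference in infection share turns a true GMT ratio of 1 into R^(−0.10): 0.84 to 0.89 without waning, 0.69 to 0.77 with it.

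**Late enrichment.** Section 6.3.1 targets 450 of the 720 participants for transfer to Cohort 2. Suppose 10% (72 of 720) have NAAT-confirmed infection, all 450 transfer, transfer is even across naïve status and nobody else is lost. Then 72 of 270, about 27%, of those sampled at D292 and D387 are infected. The GMT is multiplied by 3.29^0.267 = 1.37 to 5.77^0.267 = 1.60, before any waning.

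**The case against.** The strongest reply is that this belongs to the SAP. Section 9.4 calls itself a summary, Section 9.4.2.1.4 refers further details to the SAP, and Section 9.3 allows extra PPAS criteria after deviation review. The SAP may well add a rule, so its absence there cannot be inferred. But the protocol does more than stay silent. It names the set, applies it to every visit, and names supportive sets with the same limit. The point concerns that stated choice.

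Second, the label is not false. The set is called naïve at second injection, the analysis is descriptive, and infections by group are reported separately. Following everyone regardless of infection is a legitimate description. That stands, and is why the uncensored result should be kept. It does not answer the durability question on its own.

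Third, censoring has its own bias. Sections 2.3 and 4.3 link neutralizing antibody to protection. If low-titre participants are infected more often, censoring leaves higher-titre survivors and can also make waning look slower. This stands too, so both analyses are needed.

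Fourth, the size is fragile. The ratios rest on 10 and 12 non-naïve participants infected before vaccination and sampled 21 days after one dose. Holding the naïve GMT fixed, the confidence limits in Table 4.6 give ratios of 2754/2938 = 0.94 to 104000/2938 = 35 at 5 µg, and 3175/3961 = 0.80 to 53540/3961 = 13.5 at 10 µg.

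A reader might infer three stronger points that the documents do not support:

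- **The primary D36 result is compromised.** Only 14 days are exposed, and infection before V02 is a definitive contraindication (DCI04).
- **The Supplemental Cohorts share the fault.** Their booster arms are analysed without a naïve label (Table 9.2), and Tables 8.2 and 8.3 contain no serial Elecsys anti-N test.
- **Outside vaccination is censored throughout while infection is not.** The cut-off in Section 4.1.1 is stated for the primary analysis, and the PPAS exclusion applies only before D36.

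**Conclusion.** The point holds for the secondary naïve analyses of the Original Phase II Cohort from D78 to D387. Under the rule as written, titres after a post-D22 infection count as naïve-set titres in the main analysis and in every supportive naïve set.

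The mechanism follows from the text; the size does not. It depends on infection shares the protocol does not give and on imprecise titre ratios from a different sequence of infection and vaccination. With those ratios, 10% infected means roughly 1.13- to 1.19-fold inflation before waning of the uninfected, and up to about 1.45-fold under the extreme waning case. Enrichment at D292 and D387 is plausible from E17 and the skipped visits, but its extent depends on how many participants transfer.

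This should be corrected before the late results are interpreted as durability. It gives no ground for doubting the D36 results or the Supplemental Cohort analyses.

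**What to change.** Add to Section 9.4.2.1.4: for D78 to D387, naïve-set titres and binding concentrations are analysed only from samples taken before the first post-D22 anti-N positive sample or positive NAAT, whichever is earlier. Present the uncensored PPAS and FAS naïve results alongside, because censoring at infection can be informative, and give the number censored per visit and dose group. Agreement between the two supports the durability reading; divergence shows how far it depends on infection.

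No change is needed to the D36 analysis or to the Supplemental Cohorts.

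The cost is one or two sentences and some programming. No new samples or assays are required. The price is fewer observations at late visits, where transfer to Cohort 2 already thins the set, and a censored estimate that may itself be selective.

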9.4.2.1.5 Exploratory – Immunogenicity

Details of the exploratory analysis will be described in the SAP or supplemental SAP.

9.4.2.2 Supplemental Phase III Cohorts

9.4.2.2.1 Primary - Immunogenicity

Due to the nature of immunogenicity titer, logarithm transformation of the individual data (titers or concentrations) ($\log_{10}(\text{data})$) will be calculated and assumed to be normally distributed. The statistical inference will be based on the use of the two-sided 98.3% CI (Supplemental Cohorts 1 and 2) for non-inferiority of difference in means of post-vaccination \log_{10} transformed concentrations between the 2 groups with normal approximation.

The calculation of the CI for the GMT ratio between Booster Arms and the Comparator Group for Supplemental Cohorts 1 and 2 will use Welch's t-interval.

For the geometric mean of individual titer ratios post-boost versus pre-boost for superiority testing, the two-sided 98.3% CI (Supplemental Cohorts 1 and 2) of post-booster versus pre-booster will be calculated using \log_{10} -transformed titers assume normal distribution by applying paired t-interval.

The PPAS will be utilized for primary immunogenicity objectives. The primary immunogenicity endpoints will also be evaluated in the FAS ([Table 9.2](#)).

Subgroup analyses, where applicable, will be performed by age group (18-55 years old and ≥ 56 years old) for Intervention Groups, by priming vaccine (Supplemental Cohorts 1 and 2), and by priming platform (Supplemental Cohorts 1 and 2), in addition to the Overall Group.

Table 9.2: Analysis set used in analyses

Cohort	Intervention Group(s)	Comparator Group
Supplemental Cohort 1	PPAS, FAS	PPAS Naïve at D01+D22, FAS Naïve at D01, FAS Naïve at D01+D22

Supplemental Cohort 2	PPAS, FAS	PPAS Naïve at D01+D22, FAS Naïve at D01, FAS Naïve at D01+D22
-----------------------	-----------	---

9.4.2.2.2 Primary - Safety

The main parameter will be described for all safety endpoints. The percentage of participants (using as denominator the number of participants) will be provided for analysis of solicited AEs, unsolicited AEs (including immediate systemic AEs within 30 minutes), SAEs, AESIs and MAAEs. The corresponding 95% CIs for the percentages will be calculated based on the Clopper-Pearson method. In the priming vaccine groups (comparator for Cohorts 1 and 2), subgroup analyses will be performed by age group (18-55 years old and \geq 56 years old), high-risk medical conditions group, and baseline SARS-CoV-2 naïve status for the main safety analyses. In the Booster Groups (in Cohorts 1 and 2), subgroup analyses will be performed by age group (18-55 years old and \geq 56 years old), high-risk medical conditions group, priming vaccine platform, and individual priming vaccine. Safety endpoints will be analyzed for each of the CoV2 preS dTM primary series dosages administered in the Original Phase II Cohort (ie, 5-10-15 μ g). The SafAS population will be used for safety analyses for the following endpoints:

- Presence and relationship of unsolicited (immediate) systemic AEs reported in the 30 minutes after each vaccination.
- Presence, time of onset, number of days of occurrence, intensity, action taken, and whether the reaction led to early termination from the study, of solicited (pre-listed in the participant's DC and CRF) injection site reactions and systemic reactions occurring up to 7 days after each vaccination.
- Presence, nature (MedDRA SOC and PT), time of onset, duration, intensity, relationship to vaccination, and whether the event led to early termination from the study of unsolicited AEs reported up to 21 days after the last vaccination.
- Presence, nature (MedDRA SOC and PT), time of onset, seriousness criteria, relationship to vaccination, outcome, and whether the event led to early termination from the study, of SAEs.
- Presence, nature (MedDRA SOC and PT), relationship to vaccination of all protocol-specified AESIs from the time of the first study vaccination throughout the study.
- Presence, nature (MedDRA SOC and PT), relationship to vaccination of MAAEs throughout the study.

